# **E. STUDY GUIDELINES**

# **Patient Population**

Subjects will be patients aged 18-70 that have been evaluated by a multimodality team including a surgeon, nutritionist, and psychiatrist then scheduled for a robotic assisted gastric bypass and

sleeve gastrectomy. Once surgery has been approved patient will be considered for the study if they have no prior history of midline laparotomy and are having a de novo gastric operation.

# F. CLINICAL EVENTS

# Risks

Risks to the patient are the same as the baseline procedure with Carter- Thomason® - visceral injury, hematoma, hernia, pain. There is no foreseeable additional risk when using the neoClose® device over the baseline treatment.

# **Adverse Events (AEs)**

AEs clinically relevant to the patient will be recorded from the perioperative period through the sick week follow up period.

The following is a non-comprehensive list of possible adverse events:

- Hematoma or bleeding at port site.
- Iatrogenic visceral injury during port closure.
- Seroma at port site.
- SSI at port site.

# G. ETHICAL AND REGULATORY CONSIDERATIONS

# Confidentiality

Data that will be gathered for the study will be de-identified to protect patient information. Research charts and video recordings would be stored in a room under lock and key. No identifying markers would be included in the video recording of subjects in the study. Only the PI and designated staff would have access to the charts and video recordings. The video recordings will be kept for a maximum of 3 months to give ample time for review and analysis. The video recording will then be disposed in a manner that is according to UTHealth policy. Electronic security measures would also be taken. These are all done to minimize the inherent risk of breach of confidentiality.

# **Informed Consent**

The background, purpose and potential risks and benefits of the proposed study will be explained to each subject under the care of the investigator. Subjects will be informed of their right to withdraw from the study at any time and for any reason without sanction, penalty, or loss of benefits to which the subject is otherwise entitled, and that withdrawal from the registry will not jeopardize their future medical care.

#### **APPENDIX 1**

#### Post Operation Data Form (Day1)

Study ID:	Date:
Date of Surgery:	Duration of Surgery (min):
No. of sutures to complete suture:	Duration to complete closure:
Length of Hospital Stay:	

Pain Medication (in Hospital) and dosage:\_\_\_\_\_ Pain Evaluation:

					alog S		,			
0	1	2	3	4	5	6	7	8	9	10
							_	1		worst
no ain								Ç.,		possible pain

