# SYNOPSIS

Study Title	Randomized Trial Evaluating Effectiveness of neoClose ® Abdominal Closure Device versus CarterThomason ® Needle Passer
Trial Design	A randomized trial intended to compare neoClose ® abdominal closure versus standard Carter- Thomason ® closure in a bariatric surgery gastric bypass and sleeve gastrectomy population. The primary objective of the study is to compare the technical effectiveness of the devices. A secondary outcome will be analysis of pain scores associated with the distinct closures.
	The study will be by a group of 6 Bariatric / General Surgeons at a high volume academic institution. Patients will be randomized upon induction of anesthesia and blinded to the closure technique performed. Video analysis of technical effectiveness will be performed as well as clinic follow up at 1 week ,6 weeks and 1 year after the procedure to assess pain scores. In addition, an abdominal ultrasound will be completed at 6 weeks and 1 year to evaluate the incidence of port site hernia.
Procedure	Both devices will be used to close 12 mm camera and stapler port sites upon completion of a robotic assisted laparoscopic gastric bypass and sleeve gastrectomy. The procedure requires a 12 mm port be placed in the midline approximately 3 cm cephalad to the umbilicus and a second in the right mid abdomen. Port sites will be closed as defined as the inability to palpate a fascial defect .

Study Population	Adults aged 18-70 years with BMI > 35 that have completed a multimodality bariatric workup (EGD, nutrition evaluation and psychological evaluation) and selected to have an elective gastric bypass and sleeve gastrectomy. Subjects who fail to complete extensive pre-operative work up including endoscopic surveillance, nutrition visit, psychological clearance will be excluded from the study. A pregnancy test will be done on female subjects as part of Standard of care. There will be 35 patients per group. A power analysis was completed using the data derived from our preclinical porcine study using primary endpoint of time (32 seconds for Carter- Thomason® and 18.5 seconds for neoClose®). The alpha utilized was 0.05. A total of 70 patients will be screened for the study.

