Assessments	
 
The study will allow for the evaluation of technical effectiveness and analysis of pain scoring:
 
Technical Effectiveness 
 
Number of sutures required to complete closure.
 
Time required to complete closure.
 
Depth of needle penetration to complete closure.
 
Evaluate for surgical site occurrences immediately post op as well as at 1 ,6 weeks and 1 year after closure procdure.
 
Evaluation for port site hernia at 6 weeks with abdominal ultrasound.
 
 
 
Pain Evaluation 
 
Visual analog pain scale will be used to assess pain at both port sites.
 
Amount of intravenous narcotics required during hospitalization.
 
Hospital stay duration.
 
 
 
The study will allow for assessment of pain scores during hospitalization and at follow up visits approximately 1 week ,6 weeks and 1 year.
 

Data Collection	During the procedure, an independent examiner will record the amount of time and number of suture passes to obtain port site closure. In addition, an independent review of video from each procedure will be completed to record the time and depth of needle exposure. Patients will fill out pain analog scores

	during hospital stay and follow up visits. Care givers on the floor and in clinic will
	be blinded to the closure technique.
	Hospital records will be reviewed to record narcotic requirements.

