#### **Data Collection**

An autonomous recorder will document the number of sutures required to close each port site as well as the time required to obtain closure during the procedure. A video will be created of each procedure followed by careful analysis of the film by an independent reviewer to record the time of needle exposure to the abdominal cavity as well as depth of needle passage.

Each patient will be placed upon a Dilaudid pain pump immediately after the procedure and transitioned to oral narcotics upon initiation of liquid diet. Analog pain scoring will be completed on each hospital day as well as clinic visits approximately 1,6 weeks and 1 year after the operation. In addition, after patient discharge, the amount of narcotics required during hospitalization will be recorded. An abdominal ultrasound will be completed at 6 weeks and 1 year after the operation to evaluate the incidence of trocar site hernias.

The data will be stored on a password protected UT supplied computer in Excel files by MRN and without names. Upon analysis of the data, the MRN will be deleted thereby erasing all potential patient identifiers.

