# **D. STUDY OBJECTIVES**

# **Primary Outcome Measure**

To compare technical effectiveness of neoClose® device versus classic Carter- Thomason® suture passer. This will completed by comparing:

- Time required to complete port closure.
- Number of sutures required to complete port closure.
- Time needle is within abdominal cavity.
- Depth of needle into the abdominal cavity.
- Evaluation of surgical site occurrences.
- Evaluation of trocar site hernia incidence with abdominal ultrasound.

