# Follow-up Visit Data Form

Study ID:	Date:
Date of Surgery:	Follow up visit no. :

Pain Medication and dosage:\_\_\_\_\_ Pain Evaluation:

\_

	1 2 L I	3	4	5 	6 	7	8 	9	10 worst
no pain									possible pain

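### The plan states pain at both closed ports and sutures at each, but the forms as shown have one pain scale naming no port and single suture and time blanks

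*Combined protocol and SAP*

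**What the plan says.** Two large ports are closed in each patient. The Synopsis (Procedure) states: "Both devices will be used to close 12 mm camera and stapler port sites".

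For pain, the Synopsis (Assessments) states: "Visual analog pain scale will be used to assess pain at both port sites". Secondary Outcome Measures in section D also lists visual analog pain, but names no port.

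For the operation itself, section B (Data Collection) has a recorder "document the number of sutures required to close each port site as well as the time required to obtain closure during the procedure". The suture count is explicitly per port. Closure time is per port by the natural reading of the same sentence.

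Appendix 1 shows two forms:

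- **Day 1 form:** one suture blank ("No. of sutures to complete suture"), one closure-duration blank with no unit, length of stay, in-hospital pain medication, and one 0-10 pain scale.
- **Follow-up form:** identifiers and dates, visit number, pain medication, and one 0-10 scale under "Pain Evaluation".

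No other data form is shown or mentioned.

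**The concern.** The case for the new device is partly local. Section A argues that the width of the suture placed with the comparator can compress peritoneum and trap nerves, causing pain at the port site. Pain at the two closed ports is the measurement that tests this. A patient handed a single scale with no site named may well rate pain overall. After six trocars and gastric stapling, that rating includes four trocar sites that are not closed with either device, and visceral pain. If so, the score carries only part of any device effect.

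Patient-scored pain is also the one item here with no second source. Sutures and time have an intra-operative observer, and each procedure is filmed. If a patient was not asked about a particular port on the day, no chart review can supply the rating later.

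**Working it through.** The point is settled by setting the stated measurements beside the form fields. The plan gives no figure to reproduce.

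| Item | Stated in the plan | Shown on the form |
|---|---|---|
| Pain, Day 1 | both port sites (Synopsis) | one scale, no port visible |
| Pain, follow-up | both port sites (Synopsis); no port named (section D) | one scale, no port visible |
| Suture count | each port site (section B) | one blank, no port |
| Closure time | with the suture count (section B) | one blank, no port, no unit |

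**Count of fields.** Inputs: 35 patients per group in two groups (Synopsis, Study Population) and two closed ports per patient (Synopsis, Procedure). I assume one Day 1 form per patient, which the documents do not state.

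- Patients: 2 × 35 = 70.
- Closures: 70 × 2 = 140, against 70 suture blanks and 70 time blanks.
- Pain scores per patient over the three clinic visits: 3 × 2 = 6 port scores, against 3 scales.

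**Can the loss from a general score be sized?** The documents give no pain difference, no pain SD and no indication of how much of a port-site effect a general score would carry. To show how far the answer moves with these unknowns, I assumed a true port-site difference of 1.0 point and the same SD for either kind of score. I took 35 per group and two-sided alpha 0.05. With d = (1.0 × fraction retained) / SD and noncentrality d × √(35/2), noncentral t power is:

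| Assumed SD | Full difference | Three quarters retained | Half retained |
|---|---|---|---|
| 1.5 | 0.785 | 0.541 | 0.280 |
| 2 | 0.541 | 0.340 | 0.178 |
| 3 | 0.280 | 0.178 | 0.106 |

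The direction is clear: if a general score carries less of the effect, power falls. The amount is set entirely by the assumptions, so no cell in this table is an estimate for this trial.

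**The case against.** **The forms may work better than they look.** The suture and time entries are open blanks that can hold two values, and nothing rules out one form per port. The observer is already told to count sutures by port, and the data go into Excel files. This stands: a reader might infer that the forms make per-port data impossible to collect, and the documents do not support that. What remains is that nothing on the form asks for two values, so different staff could enter a sum, a mean or one port only.

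**The scale graphics are damaged in the text available.** A port label inside the graphic cannot be excluded. This stands as a limit on the pain part. The typed suture and time fields are intact and single.

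**No wording put to the patient is shown.** The Synopsis says both port sites, and staff might ask accordingly. It is therefore likely, not certain, that patients would rate general pain.

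**The between-arm comparison does not need port-level sutures or time.** Each patient is randomized to one device, so a per-patient total supports a valid two-group test, provided every form records the same quantity. This is a fair reason to treat pain as the core of the point.

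**Site occurrences and hernia.** Section D lists "Evaluation of surgical site occurrences" and "Evaluation of trocar site hernia incidence with abdominal ultrasound", and neither form has a field for them. A reader might infer that these too are per-port outcomes with nowhere to be recorded. The plan does not explicitly make them per port. Adverse Events (section F) calls for recording events and names port-site hematoma, seroma and infection, and ultrasound findings can be held in a report. The adverse event window does appear to end before the 1 year visit, so it does not cover every check listed in the Synopsis.

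**Pain is secondary.** The sample size was based on closure time. A reader might take a particular fall in power for pain as shown; the inputs are assumed throughout, so it is not.

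**Conclusion.** The forms as shown do not match the per-port pain and suture measurements stated in the Synopsis and section B, and section D leaves the port unstated for pain. If they are used as printed, port-site pain would not be reliably collected, and what is missed cannot be restored afterwards. The firm size of the gap is one scale where two scores are needed, plus one suture blank and one time blank for two closures. Its effect on the pain comparison is probably dilution, of unknown amount.

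This rests on three assumptions: the graphics carry no port label, staff do not routinely ask by port, and these are the forms in use. It is a modest point about a secondary outcome and about consistent recording of sutures and time. It does not invalidate the between-arm comparison. It is worth acting on because the remedy is nearly free and must be in place before patients are scored.

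**What to change.** 1. First reconcile the port descriptions, so that the labels match the ports actually closed. The Synopsis places the second 12 mm port in the right mid abdomen, and the gastric bypass text in section B places it in the right mid clavicular line. The sleeve gastrectomy text says trocar number and locations are the same, yet refers to a 15 mm port in the right upper quadrant.
2. On both forms, print one 0-10 pain scale per closed port, labelled by site.
3. On the Day 1 form, print one row per closed port for number of sutures and closure time, with the unit of time.
4. Reword the pain item in Secondary Outcome Measures so that it names the port sites, as the Synopsis does.
5. Optionally, add a site-occurrence tick box to the follow-up form for the 1 week, 6 week and 1 year checks. This is a convenience, not a necessary correction.

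The cost is a revised form and a few seconds more per visit, with no added staff or procedure.

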# Follow-up Visit Data Form

Study ID:	Date:
Date of Surgery:	Follow up visit no. :

Pain Medication and dosage:\_\_\_\_\_ Pain Evaluation:

\_

	1 2 L I	3	4	5 	6 	7	8 	9	10 worst
no pain									possible pain
